12.0 MEASUREMENT OF RESPONSE

Tumor Clearance

A patient will be considered to have a complete response if there is no measurable or palpable tumor either on clinical or radiographic (CT-PET scan) examination assessed within 3 months after the completion of treatment. Complete response will be defined as complete disappearance of disease or residual radiographic abnormality that is not considered to be tumor.

13.0 CRITERIA FOR DISCONTINUATION OF TREATMENT

Unacceptable adverse event(s), intercurrent illness which prevents further administration of treatment, patient preference, progressive disease, life threatening or other unacceptable drug-related toxicity, changes in the patient's condition that render the patient unacceptable for

further treatment in the judgment of the investigators.

14.0 DRUG INFORMATION: CETUXIMAB

14.1 Formulation: Cetuximab is an anti-EGFR receptor humanized chimeric monoclonal antibody. Cetuximab is expressed in SP2/0 myeloma cell line, grown in large scale cell culture bioreactors, and purified to a high level purity using several purification steps including protein A chromatography, ion exchange chromatography, low pH treatment, and nanofiltration. Cetuximab is not known to be a vesicant.

14.2 Supply: The product is formulated to 2 mg protein/mL with phosphate buffered saline, pH 7.2 ± 0.2 and aseptically filled into sterile glass vials, 100 mg per 50 cc vial, and stored as a liquid at 2 to 8° C. Each vial contains the following active and inactive ingredients per 1.0 ml: 2 mg of cetuximab, 145 nmol/L sodium chloride, and 10 mmol/L sodium phosphate.

14.3 Safety Precautions: Appropriate mask, protective clothing, eye protection, gloves and Class II vertical-laminar-airflow safety cabinets are recommended during preparation and handling.

14.4 Preparation and Administration:

14.4.1 Cetuximab is available commercially as an injectable solution, in single-use, ready-to-use 50-mL vials containing 2 mg/mL of product. Cetuximab requires no dilution. Cetuximab should not be mixed with or diluted with other drugs or solutions for infusion such as 5%-glucose.

14.4.2 The dose and volume of the study drug to be infused are dependent upon the patient's actual BSA. The infusion rate must never exceed 10 mg/minute (5 mL/minute). The dose may subsequently be reduced for individual patients, depending on a patient's toxicity. For the duration that patients are on cetuximab therapy, adverse event monitoring should be done continuously. Patients will be evaluated for adverse events at each visit and are to be instructed to call their physician to report any adverse events between visits.

14.4.3 Cetuximab may be administered via an infusion pump or syringe pump. Cetuximab administration requires an in-line low protein-binding 0.22 micron filter. Note: one filter per dose should be sufficient, but further filters can be used if a filter becomes blocked.

Administration via Infusion Pump

Calculate the appropriate volume of cetuximab based on the dose and using an appropriate sterile syringe (min 50 mL) draw up the required volume from the vial(s). Add the cetuximab into a sterile evacuated container or bag (glass administration containers are not recommended). Do not shake. Attach an infusion line with a low protein binding 0.22 micron in-line filter.

Use an infusion pump for administration. Set and control the rate as noted above and infuse the whole dose.

Administration via Syringe Pump

Calculate the appropriate volume of cetuximab based on the dose and using an appropriate sterile syringe (min 50 mL) draw up the required volume from the vial(s). Do not shake. Remove the needle, and put the syringe into the syringe pump. Attach tubing with a low protein-binding 0.22 micron filter. Set and control the rate as described above. Make sure that the whole dose has been infused.

Studies have been conducted to demonstrate the compatibility of cetuximab drug product with various infusion systems. Some examples of materials, IV containers, infusion sets, and filters tested and recommended for use with cetuximab are listed below. For further examples of approved materials, please see the Investigator Brochure.

Recommended IV Containers

- IntraVia™ IV Bag with PVC Ports, Model No. 2J8002 (Baxter Healthcare Corporation)
- EVA™ IV Bag, Model No. 2B8152 (Baxter Healthcare Corporation)
- LifeCare™ IV Bag, Model No. 7951-12 (Abbott Laboratories)

Recommended Infusion Sets

- Vented Continu-Flo Solution Set™, Model No. 2C6541s (Baxter Healthcare Corporation) to be used with an in-line filter set, Model No. 2679 (Abbott Laboratories)
- Vented Paclitaxel Set™ with 0.22- μ m downstream high-pressure in-line filter, Model No. 2C7553 (Baxter Healthcare Corporation)

Recommended Filters

- Vented Continu-Flo Solution Set™, Model No. 2C6541s (Baxter Healthcare Corporation) to be used with an in-line filter set, Model No. 2679 (Abbott Laboratories)
- Intrapur Plus (B. Braun AG) reference number 409 9800
- Poly-lined filtered Extension set (Alaris Medical Systems) reference number C20350

14.4.4 Normal saline should be used to clear the infusion set of residual cetuximab. The delivered drug product is >95% for all recommended infusion sets when flushed with 50 mL of normal saline. Use a separate line for cetuximab infusion.

14.4.5 Storage Requirements/Stability: Cetuximab must be stored under refrigeration at +2°C to +8°C (+36°F to +46°F). DO NOT FREEZE CETUXIMAB. Drug supplies must be kept in a secure, limited access storage area under the recommended storage conditions. Once cetuximab is removed from the vial, the recommended maximum storage time in the infusion

container or syringe is 8 hours at room temperature or 12 hours in the refrigerator.

15.0 EGFR ANALYSIS

The primary goal of this analysis is to determine whether cetuximab given at the clinically recommended dose will affect EGFR, phospho-EGFR and down-stream signaling within the tumor as well as in the normal mucosa. The protein levels of EGFR, pY845-EGFR and various down-stream signaling molecules will be measured by immunoblotting as well as immunohistochemical analysis in both normal and tumor samples at baseline and post-treatment as described previously (26).

15.1 Pre-Therapy Tumor Sample Collection and Initial Processing

The initial pre-treatment punch-biopsy specimen for research (about 3x3x3 mm) of the tumor and mucosa cells (or a buccal swab) will be collected in ice cold saline containing a cocktail of protease (Roche Diagnostic Co., Indianapolis, IN) and phosphatase inhibitors (Sigma, St. Louis, MO) in the presence of laboratory personnel from [name] laboratory. The sample will be divided into 2 parts. The first part will be fixed in 10% phosphate buffered formalin and will be stored in paraffin blocks for immunohistochemistry, and second part will be used to extract proteins for immunoblotting.

15.2 Method of Assessment of EGFR Expression in Tumor After Cetuximab Loading Dose

At the time of the second biopsy a tumor specimen (about 5x5x5mm) along with buccal swab will be collected. The tumor specimen will be divided into 3 parts. The first two parts will be processed as described in section 15.3.1. When feasible the 3rd part will be used to isolate RNA in [name] laboratory. EGFRvIII expression and p53 mutation analysis will be assessed on cDNA obtained from total RNA converted with RT-PCR.

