15.3 Sample Preparation and Analysis

15.3.1 High-throughput immunoblotting and isolation of RNA and DNA for genetic studies:

Tumor samples will be processed immediately for protein extraction in [name] laboratory. A total of 200 µg total protein will be subjected to electrophoresis on a 2D 4 to 12% bis-tris precast gel (Invitrogen, Carlsbad, CA) and transferred onto a PVDF membrane. A Miniblotter 28 dual system (Immunetics, Cambridge, MA) will be used to probe all the antibodies in duplicate. After incubating the membrane with different antibodies overnight, membranes will be washed and probed with horseradish peroxidase conjugated IgG (Cell Signaling Technology, Beverly, MA), diluted 1:5,000 in TBST for 1 hr at room temperature; the antigen—antibody complexes will be visualized by enhanced chemiluminescence (ECL-Plus; GE Biosciences, Piscataway, NJ). The films then will be scanned, and the bands analyzed using NIH ImageJ software. Proteins to be assessed include phospho and total forms of EGFR, AKT, Src, STAT3, in addition to total p27, PARP, Bel-X_L will also be assessed.

Isolation of DNA (from the FFPE pretreatment diagnostic biopsy) and RNA (from the research biopsy when possible) will be carried out using DNAeasy and RNAeasy (both from Qiagen) on the remaining sample according to the manufacturers instructions.

15.3.2 Immunohistochemistry and Scoring of TMA:

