One high-density TMA will be constructed using a manual tissue arrayer (Beecher Instruments, [name], USA) at the core facility at the University of Michigan using standard methods. Tissue cores from the regions of interest (tumor tissues, before and after treatment) will be targeted for transfer to the recipient array block. At least three 0.6 mm diameter replicate tissue cores will be sampled from each subregion of the selected sample. The final TMA will consist of approximately 160 cores. After construction, 4 gm sections will be cut, and hematoxylin and eosin staining will be performed on the initial slide to verify the histology. Serial 4 gm sections will be further cut and transferred to positively charged slides, these sections will be subjected to standard immunohistochemical staining procedures. [name] lab have validated both total and phospho-antibodies that can be used successfully on formalin fixed tissue (26). The stained test slides will be reviewed by the head-and-neck pathologist co-investigator ([name]) for the expected pattern and appropriate intensity. The information about expected and appropriate staining for each antibody will be discussed with the other investigators to confirm the scoring criteria. The TMAs will be then stained by the staff at the Tissue Core. Each tissue core will be scored by a board certified oral and maxillofacial pathologist who is blinded as to the identity of the cores. Each tissue core will be scored for intensity of SCC cells staining: 1, undetectable; 2, weak; 3, moderate; 4, strong. Multiple TMA core measurements from the same subject will be averaged. This average score in its continuous scale will be used in all analyses.

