20.3.2 Secondary Objectives

20.3.2.1 *To characterize the changes tumor EGFR, pEGFR, downstream signaling following a loading dose of cetuximab.*

Markers to be analyzed include, but are not limited to, EGFR and pEGFR. Some are measured on a continuous scale, and some on an ordinal scale. Continuous scale variables will be expressed as percent change from baseline, and the distribution will be characterized graphically (e.g., boxplot) and by descriptive statistics. After possible transformation (e.g., logarithmic), a single sample t-test will be used to evaluate the null hypothesis that the mean change equals 0. The percent change will be related to tumor control, progression-free survival, and the various assessments of toxicity by linear regression, logistic regression, or proportion hazards (Cox) regression, as appropriate. Ordinal scale variables will be expressed as difference from baseline, followed by a similar analysis plan to relate the differences to clinical outcomes. Because this is a secondary objective, all of the analyses will be guided by descriptive displays of the data.

20.3.2.2 *Compare normal mucosa EGFR to EGFR in the tumor sample.*

Repeated measures linear models will be used to characterize the change in differences between normal mucosa and tumor EGFR across the loading dose of cetuximab and determine if there are significant demographic or clinical variables that affect that change.

20.3.2.3 *To explore if baseline EGFR, BclxL, p.53 and p16 tumor expression are related to treatment response.*

The distributions of these markers in all patients, and in patients who do and do not respond, will be characterized by descriptive statistics (e.g., mean, median) and graphics (for example, boxplots). Because the number of treatment failures is likely to be small, these analyses will be considered strictly exploratory.

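### Section 15.2 sends the post-cetuximab biopsy to a processing section with no formalin step and no inhibitor medium, so the planned post-dose immunohistochemistry has no fixed tissue and the two biopsies are not handled alike as written

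*Combined protocol and SAP*

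**What the plan says.** For the baseline research biopsy, section 15.1 is specific. The tumor and mucosal material "will be collected in ice cold saline containing a cocktail of protease" and phosphatase inhibitors, with laboratory staff present. The sample is then split in two: "The first part will be fixed in 10% phosphate buffered formalin and will be stored in paraffin blocks for immunohistochemistry", and the second part goes to protein extraction for immunoblotting.

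For the post-dose biopsy, section 15.2 gives only timing and size: "At the time of the second biopsy a tumor specimen (about 5x5x5mm) along with buccal swab will be collected". It divides the tumor specimen into three parts. Of these, "The first two parts will be processed as described in section 15.3.1", and the third goes to RNA isolation when feasible.

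Section 15.3.1 begins "Tumor samples will be processed immediately for protein extraction" and continues with the gel, the blot and DNA/RNA isolation. Its one mention of fixed tissue concerns the pretreatment diagnostic biopsy, as a source of DNA.

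Section 15.0 plans immunoblotting and immunohistochemistry at both time points. For the tissue microarray, section 15.3.2 says: "Tissue cores from the regions of interest (tumor tissues, before and after treatment) will be targeted for transfer to the recipient array block".

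For the analysis, section 20.3.2.1 says that after possible transformation "a single sample t-test will be used to evaluate the null hypothesis that the mean change equals 0". No significance level is given for that test.

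**The concern.** Two things follow from the cross-reference in 15.2.

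The first concerns feasibility. Half of the tissue for the before-and-after immunohistochemistry is never created if the laboratory follows the text.

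The second concerns comparability. A phospho-protein comparison within patients depends on both specimens being preserved in the same way. The protocol specifies phosphatase inhibitors at baseline, so it treats preservation as necessary, yet it states none after the dose. The trial has one arm and tests the mean change against zero, so a systematic handling difference between visits cannot be told apart from a drug effect.

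The paired tissue also matters to the design: section 20.1 enrolls 43 patients in order to have 36 who complete radiation and have both biopsies.

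**Working it through.** The plan states no figure on this point, so the check is mainly a comparison of sections.

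**1. Handling of the two specimens as written**

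| Step | Baseline research biopsy (15.1) | Post-dose biopsy (15.2, then 15.3.1) |
|---|---|---|
| Collection medium | Ice-cold saline with protease and phosphatase inhibitors | Not stated |
| Part 1 | Formalin, paraffin, for immunohistochemistry | Protein extraction and blot (15.3.1) |
| Part 2 | Protein extraction | Protein extraction and blot (15.3.1) |
| Part 3 | None | RNA, when feasible |
| Fixed tissue available | Yes | None |
| Buccal swab medium | Same inhibitor saline | Not stated |

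**2. Against what the plan requires.** Sections 15.0 and 15.3.2 need fixed tumor tissue from after the dose. The three parts in 15.2 supply none. This needs no assumption about signal loss.

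**3. What was meant.** The only two-part split into a fixed part and a protein part is in 15.1. The words in 15.2 about the first two parts fit that split, so 15.3.1 is very probably a wrong reference for 15.1.

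**4. Direction of any bias.** If the baseline is a research biopsy protected by inhibitor and the post-dose sample is not, loss of phosphorylation would lower the post-dose value and look like inhibition. But 7.5.2 takes a baseline research biopsy only when no suitable clinical specimen exists; a biopsy done at the institution within 30 days of consent is suitable. No inhibitor handling is stated for such specimens. In those pairs the baseline may be the less protected sample, and the bias could run the other way.

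**5. Size, as illustration only.** The documents give neither a handling loss nor an SD. Assume no drug effect, n = 36 pairs, and a handling shift of d standard deviations of the change. The rejection probability is that of a two-sided one-sample t-test with 35 degrees of freedom and noncentrality d × √36 = 6d. The level is also an assumption: 0.05, or 0.20 as in the primary tests.

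| Assumed d | Level 0.05 | Level 0.20 |
|---|---|---|
| 0 | 5% | 20% |
| 0.1 | 9% | 28% |
| 0.2 | 22% | 47% |
| 0.3 | 42% | 69% |
| 0.5 | 83% | 95% |

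An observed mean shift reaches significance at 2.030/6 = 0.34 SD (level 0.05) or 1.306/6 = 0.22 SD (level 0.20). The table shows how sensitive the test would be to a shift. It does not show that a shift exists.

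**6. Other analyses.** With a uniform proportional loss L, percent change x (as a fraction) becomes (1 − L)(1 + x) − 1 = (1 − L)x − L, a linear rescaling. On the log scale it is a constant shift. The slope test in a linear, logistic or Cox regression on that marker is unchanged; a loss that varies between patients would add noise. The tumor-versus-mucosa model in 20.3.2.2 names EGFR, not phospho-EGFR. The post-dose swab also has no stated medium, so a loss common to both tissues would partly cancel in the difference.

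**The case against.** The strongest reply is that this is a typing slip in a cross-reference. Sections 15.0 and 15.3.2 show that common handling was intended, and 7.5.2 sends both research biopsies straight to the same laboratory. Section 15.2 omits the medium; it does not tell anyone to leave inhibitors out. Section 15.0 also refers to a previously published method, which may carry the handling details and cannot be checked here. Section 15.3.1 calls for immediate processing, which shortens the time for loss.

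Most of this stands. It makes the slip reading likely and a large handling loss less so. It does not supply a fixed post-dose block, and prompt extraction does not replace inhibitors. The written procedure is also what an audit under section 19.0 would compare practice with.

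A reader might infer more: that only the post-dose sample is exposed to loss, so that handling would mimic the inhibition hypothesised in section 2.0 and contaminate every marker analysis. The documents do not support that. A clinical baseline specimen has no stated protection either, no loss is quantified, and steps 4 and 6 show that the direction is not fixed and that the regressions and the mucosa model are not affected in the way supposed.

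**Conclusion.** The cross-reference in 15.2 is wrong as written and should be corrected. The firm consequence is that, followed literally, the procedure leaves no formalin-fixed post-dose tumor tissue, so the post-treatment immunohistochemistry and array cores cannot be produced.

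The conditional consequence is a possible handling bias in the one-sample test of phospho-marker change in 20.3.2.1. Its size is unknown from the documents, and its direction is uncertain in pairs with a clinical baseline specimen. It also depends on the laboratory actually handling the two specimens differently.

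Only secondary objectives are touched. The primary recurrence and toxicity analyses are unaffected.

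**What to change.** - In 15.2, refer to 15.1 for collection and division: the same ice-cold inhibitor saline, part 1 to formalin and paraffin, part 2 to protein extraction by 15.3.1. Leave part 3 for RNA as it is.
- State the same medium for the post-dose buccal swab.
- Record the collection medium and the time from biopsy to processing at both visits.
- Flag every pair whose two specimens were not both collected in inhibitor, including pairs with a clinical baseline specimen. Repeat the phospho-marker change analysis without them as a sensitivity analysis. Excluding them outright could remove every patient with a clinical baseline specimen, a number that the documents do not give.

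The cost is one corrected sentence and two laboratory form fields, with no added biopsy. If many patients have a clinical baseline specimen, the sensitivity analysis will be small and imprecise.

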15.3 Sample Preparation and Analysis

15.3.1 High-throughput immunoblotting and isolation of RNA and DNA for genetic studies:

Tumor samples will be processed immediately for protein extraction in [name] laboratory. A total of 200 µg total protein will be subjected to electrophoresis on a 2D 4 to 12% bis-tris precast gel (Invitrogen, Carlsbad, CA) and transferred onto a PVDF membrane. A Miniblotter 28 dual system (Immunetics, Cambridge, MA) will be used to probe all the antibodies in duplicate. After incubating the membrane with different antibodies overnight, membranes will be washed and probed with horseradish peroxidase conjugated IgG (Cell Signaling Technology, Beverly, MA), diluted 1:5,000 in TBST for 1 hr at room temperature; the antigen—antibody complexes will be visualized by enhanced chemiluminescence (ECL-Plus; GE Biosciences, Piscataway, NJ). The films then will be scanned, and the bands analyzed using NIH ImageJ software. Proteins to be assessed include phospho and total forms of EGFR, AKT, Src, STAT3, in addition to total p27, PARP, Bel-X_L will also be assessed.

Isolation of DNA (from the FFPE pretreatment diagnostic biopsy) and RNA (from the research biopsy when possible) will be carried out using DNAeasy and RNAeasy (both from Qiagen) on the remaining sample according to the manufacturers instructions.

15.3.2 Immunohistochemistry and Scoring of TMA:

One high-density TMA will be constructed using a manual tissue arrayer (Beecher Instruments, [name], USA) at the core facility at the University of Michigan using standard methods. Tissue cores from the regions of interest (tumor tissues, before and after treatment) will be targeted for transfer to the recipient array block. At least three 0.6 mm diameter replicate tissue cores will be sampled from each subregion of the selected sample. The final TMA will consist of approximately 160 cores. After construction, 4 gm sections will be cut, and hematoxylin and eosin staining will be performed on the initial slide to verify the histology. Serial 4 gm sections will be further cut and transferred to positively charged slides, these sections will be subjected to standard immunohistochemical staining procedures. [name] lab have validated both total and phospho-antibodies that can be used successfully on formalin fixed tissue (26). The stained test slides will be reviewed by the head-and-neck pathologist co-investigator ([name]) for the expected pattern and appropriate intensity. The information about expected and appropriate staining for each antibody will be discussed with the other investigators to confirm the scoring criteria. The TMAs will be then stained by the staff at the Tissue Core. Each tissue core will be scored by a board certified oral and maxillofacial pathologist who is blinded as to the identity of the cores. Each tissue core will be scored for intensity of SCC cells staining: 1, undetectable; 2, weak; 3, moderate; 4, strong. Multiple TMA core measurements from the same subject will be averaged. This average score in its continuous scale will be used in all analyses.

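### Read together, Sections 15.3.2 and 20.3.2.1 route the averaged 1-to-4 staining score to percent change from baseline, a measure that depends on the arbitrary code given to undetectable staining

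*Combined protocol and SAP*

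**What the plan says.** Section 15.3.2 places pre- and post-treatment tumor cores on one tissue microarray: "Tissue cores from the regions of interest (tumor tissues, before and after treatment) will be targeted for transfer to the recipient array block". On replication it says: "At least three 0.6 mm diameter replicate tissue cores will be sampled from each subregion of the selected sample". Each core receives one of four ordered grades: "1, undetectable; 2, weak; 3, moderate; 4, strong". The section then says: "Multiple TMA core measurements from the same subject will be averaged". It closes with: "This average score in its continuous scale will be used in all analyses".

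Section 20.3.2.1 covers change in tumor markers after the loading dose. It expects markers of both scale types but does not list which is which. For one type the rule is: "Continuous scale variables will be expressed as percent change from baseline". For the other: "Ordinal scale variables will be expressed as difference from baseline". A one-sample t-test of mean change follows, optionally after a transformation such as the logarithm. The percent change is then related to tumor control, progression-free survival and toxicity by regression.

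Neither section recodes undetectable staining to zero or exempts the staining score from the percent-change rule.

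**The concern.** The staining score is the only ordered-category tumor measurement described in Section 15, so it is the obvious candidate for the ordinal rule. Section 15.3.2 nevertheless labels its average continuous, without exception, and 20.3.2.1 attaches percent change to that label.

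Percent change has a fixed meaning only where zero means absence. Here absence is coded 1, so the size of a change depends on where the code sequence happens to start. Dividing by a baseline that is itself measured with error also distorts the average change.

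At stake are the immunohistochemical readout of EGFR inhibition and its use as a predictor of outcome. Section 20.1 sets enrollment at 43 so that 36 patients have both biopsies, partly so that these secondary questions can be analyzed.

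**Working it through.** The plan states no figure for this analysis, so there is none to reproduce.

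**Inputs from the documents.** Codes 1 to 4, averaging, and at least three cores (15.3.2); 36 patients with both biopsies (20.1); the percent-change and difference rules, the one-sample t-test and the optional log (20.3.2.1).

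**Step 1: dependence on the origin.** Percent change = 100 × (post − pre) / pre.

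| Change | Codes 1–4 | Same slides coded 0–3 | Log ratio, codes 1–4 | Difference, either coding |
|---|---|---|---|---|
| weak to undetectable | (1−2)/2 = −50% | (0−1)/1 = −100% | −0.69 | −1 |
| moderate to undetectable | (1−3)/3 = −67% | (0−2)/2 = −100% | −1.10 | −2 |
| strong to undetectable | (1−4)/4 = −75% | (0−3)/3 = −100% | −1.39 | −3 |
| strong to weak | (2−4)/4 = −50% | (1−3)/3 = −67% | −0.69 | −2 |

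On codes 1–4, total loss never reaches −100%, and strong to weak ties with total loss from weak. Shifting every code down by one breaks that tie, although the slides are the same. Percent change from an undetectable baseline would then be undefined. On the log scale the tie remains on codes 1–4, and on 0–3 any undetectable reading has no logarithm. Only the difference is unaffected by the shift.

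These are the whole-number cases. With three-core averages, total loss runs from −25% (baseline 1.33) through −57% (baseline 2.33) to −75% (baseline 4).

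**Step 2: why percent change is biased when nothing changes.** Take two patients whose scores differ between biopsies only by measurement error, one going from 2 to 3 and the other from 3 to 2.

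- Percent change: +50% and −33.3%; mean (50 − 33.3)/2 = +8.3%.
- Log ratio: +0.405 and −0.405; mean 0.
- Difference: +1 and −1; mean 0.

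Rises from a low baseline count for more than equal falls from a high one. The bias is therefore upward, away from showing inhibition.

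**Step 3: size in a trial like this one.** Simulation with no true change: 36 pairs, three cores per biopsy held to the codes 1–4 and averaged, two-sided 5% one-sample t-test. The documents give no variability for this score. Assumed: biopsy-level SD 0.4 to 0.8, core SD 0.4, and four mixes of baseline grades.

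| Measure tested | Rejection rate (nominal 5%) |
|---|---|
| percent change, untransformed | about 7% to 18% |
| log ratio | about 4% to 5% |
| difference | about 4% to 6% |

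The mean percent change was about +3% to +12%. Since the log ratio of the same 1–4 scores holds its size, the inflation comes from dividing by a noisy baseline and not from the missing zero. The missing zero causes the origin dependence in Step 1.

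**The case against.** The strongest reply is that no sentence says outright that the staining score is analyzed as percent change. The closing sentence of 15.3.2 follows the averaging instruction and could mean only that the mean is not to be rounded or dichotomized. The ordinal rule would then still govern change, and would have a marker to apply to. That reading is possible, but neither section states it, and the word continuous is the one that triggers percent change in 20.3.2.1.

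Second, 20.3.2.1 permits a log transformation before the t-test, and this does restore the test size. That stands. It is optional, however, and it leaves the predictor dependent on the origin.

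Third, the difference also varies with baseline: total loss is −1, −2 or −3. That stands too. The difference counts steps lost and does not move with the origin, but it treats the steps between grades as equal.

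Fourth, this is a secondary objective guided by descriptive displays, and the same proteins are measured by immunoblot, where percent change is suitable. That limits the impact.

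A reader might also infer that percent change ranks patients wrongly. The documents name no correct ordering, and treating total loss from weak as strong inhibition is defensible. What can be said is that the ordering changes with the coding.

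**Conclusion.** The point holds as a conflict between two sections whose natural joint reading gives a poor measure of change. The origin dependence is plain arithmetic and needs no assumption: −50%, −67% or −75% for total loss, against −100% throughout if the same slides were coded 0–3. The upward bias of about 3% to 12% and the 7% to 18% rejection rate rest on the assumed SDs and baseline mixes and apply to the untransformed test.

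Two stronger inferences are not supported. The plan is not shown to favor a false finding of EGFR inhibition, because the bias runs the other way. Nor are the primary endpoints, the sample size or the immunoblot results affected. Averaging the cores is not at fault either. The consequence is confined to the immunohistochemical part of the secondary marker analysis, but it is worth correcting because the plan already contains a better rule.

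**What to change.** Keep the last sentence of 15.3.2, which is still needed for baseline and repeated-measures use of the mean score (20.3.2.2 and 20.3.2.3). Add after it: change in the mean staining score is expressed as the post minus pre difference under the ordinal rule of 20.3.2.1, both for the one-sample test and as the predictor in the outcome analyses. State in 20.3.2.1 that percent change or log ratio is reserved for immunoblot densitometry.

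The cost is one added sentence and a short cross-reference, with no new data, assays or patients. The small downside is that the difference assumes equal spacing between the four grades; the plan should say so.
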